### **Procedures performed for research purposes only:**

Randomization, for those participating in that arm of the study, is distinct from the us clinical care that is provided at participating clinics. In addition, the use of a LNG IUD alone for EC is unique to the study and is not currently offered at the clinics.

# Statistical Methods, Data Analysis and Interpretation

**Sample Size and Randomization:** There are two arms to the study. The main study is a randomized controlled trial with non-inferiority design and participants will be assigned 1:1 to either the copper T380 IUD or the LNG20 IUD for EC. The non-inferiority margin is 2.5% and we assume a pregnancy rate of 0.1% for copper IUD EC users and a 1% EC pregnancy rate for LNG IUD users. This estimate, based on our current COLIEC study (IRB# 50483) is conservative, falling within the 95% confidence interval (CI) of 0%-5.2% of the pregnancy rate of LNG20 IUD plus oral LNG for EC users. To achieve 80% power to detect a twosided 95% CI around the EC pregnancy incidence, a percent difference that does not cross the 2.5% noninferiorty margin, will require 335 participants per study arm (total of 670). We will recruit an additional 5%, 36 participants, (total of 706) to accommodate for potential early loss to follow up. Five percent is a conservative estimate based on our prior successful IUD EC studies. Even with obtaining multiple points of contact information and testing them prior to enrollment this can be a difficult population to maintain contact with. In our prior EC studies at 1 month we lost contact with 12 of 218 (5.5%) IUD users in our copper T IUD vs. oral LNG study and 8 of 176 (4.5%) in the COLIEC study. The use of the 2.5% noninferiority margin is within confidence intervals of previous literature for pregnancies among oral LNG users, which is one of the clinical standards of care (1.7%; 95% CI 0.8%-2.6%) (76) and the continued protection against future unintended pregnancy explored in aim 2 makes this clinically acceptable. In addition, women who currently present for EC and decline a copper IUD are left with a choice of oral EC, which also falls within this confidence interval. While approaching the higher limit of the oral LNG per cycle pregnancy rate from the aforementioned study, it is well below per cycle pregnancy events in some subpopulations using oral LNG, which can result in pregnancy events of 5.8% for women with higher BMIs (>30BMI) and 7.3% in women who have additional unprotected sexual intercourse(28). The LNG20 IUD is not affected by BMI and offers protection against pregnancy following future intercourse.

The maximum number of participants in the entire study is 706.

If recruitment is not adequate with this design and potential participants report concern about randomization as a reason for non-participation then a patient-preference cohort (PPC) will be offered to interested and qualified individuals.

All women presenting to participating clinics when study participation is offered will be presented with a study information sheet, which includes an assessment of interest in the study. If we find that we are not able to meet recruitment goals (e.g. <80 participants enrolled in the first 6 months) and the reason for non-participation is assessed to be lack of willingness to be randomized to the study interventions, then we will add an option for a PPC. Should the PPC be introduced then participants who are interested in the study and eligible for participation but not willing to be randomized will be offered participation through the PPC. While 90% of EC users enrolled in a current study where they can choose their IUD type stated they would be willing to be randomized to either type of IUD, some individuals may be reluctant to agree to random assignment. This potentially impacts result generalizability. In order to evaluate the magnitude and direction of non-participation bias we will offer eligible women presenting for EC who desire an IUD but are not willing to undergo randomization participation in a patient-preference cohort (PPC). Participants in the PPC may choose the

IUD they desire. The PPC will allow us to ascertain selection bias due to RCT nonparticipation.

### Outcomes

Primary Outcome: Emergency contraception failures in both arms as assessed by positive urine pregnancy tests (HCG >25 IU) 4 weeks after having the IUD inserted.

### Secondary Outcomes:

one-year unintended pregnancy rates

Assess the one-year continuation, satisfaction, pain, and bleeding patterns of a LNG20 IUD to a copper T380 IUC as a method of EC

- Pregnancy rates in the first year after presenting for EC
- Timing of IUD insertion relative to time in the menstrual cycle (pre-ovulatory, ovulatory, post-ovulatory)
- Unplanned pregnancy rates in the first year after presenting for EC
- Effect of IUD choice on vaginal bleeding assessed monthly by Pictorial Blood Assessment Chart
- Infections
- IUD continuation, expulsions, and removals through the first year after presenting for EC
- Satisfaction with EC method and contraception chosen
- Sexual satisfaction at baseline and through the first year after presenting for EC
- Frequency of unprotected intercourse since presenting for EC
- Use of contraception in the year following presentation for EC
- New diagnosis of any STI
- IUD related complications
- Abortion
- Contraception related side effects
- Use of a barrier method for prevention of sexually transmitted infections

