### Data Analyses:

The primary objective will be tested by non-inferiority design to test the hypothesis that the LNG IUD is no worse than the copper IUD with a noninferiority margin of 2.5%. Using Blackwelder's approach for equivalence testing,[8] comparing those who become pregnant during the menstrual cycle in which their study IUD was inserted. Noninferiority will be established if the lower bound of a two-sided 95% CI does not cross the noninferiority bound. Analysis will be by intention to treat.

For objective #2, comparison of one-year unintended pregnancy rates from women initiating the levonorgestrel IUD vs. copper T380 IUD for EC, will be assessed by Kaplan-Meier estimates. This same approach will be utilized to construct estimates of the proportion of patients who continue with their selected IUD for 1 year (continuation

proportion). Continuous variables will be assessed by t-tests and discrete variables by Chisquare testing as appropriate.

All data will be analyzed using Stata statistical software (College Station, Texas). Standard quality control methods will be employed including use of an independent data safety monitor.

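### Sexual satisfaction is listed with a baseline value, but the only method that can apply to it has no baseline term, so some precision is given up in one secondary outcome

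*Combined protocol and SAP*

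**What the plan says.** The Secondary Outcomes section has fifteen bullets. One reads "Sexual satisfaction at baseline and through the first year after presenting for EC", and it is the only one that names a baseline measurement.

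The Data Analyses section gives a non-inferiority test for the primary objective and Kaplan-Meier estimates for one-year pregnancy and continuation. Everything else falls under one sentence: "Continuous variables will be assessed by t-tests and discrete variables by Chisquare testing as appropriate". Nowhere do the documents mention a baseline covariate, a regression model, change from baseline or a repeated-measures analysis.

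The documents also do not name the instrument for sexual satisfaction, say whether the score is continuous or ordinal, or give the time point to be compared. The visit lists under Study Procedures mention sexual activity and satisfaction with the method, but not sexual satisfaction. The enrollment list says only that data are collected.

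On allocation, the statistical section states that "participants will be assigned 1:1 to either the copper T380 IUD or the LNG20 IUD for EC".

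**The concern.** When an outcome is measured before and after randomization, the baseline score usually explains part of the variation in the later score. A t-test on follow-up scores leaves that part in the error term, and a chi-square test does the same for a discrete item. The device comparison then has a wider confidence interval and less power than the same data could give. The plan says it will have the baseline value, so using it needs no extra participants.

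**Working it through.** **1. The plan's own sample size.** The inputs are in the statistical section: "we assume a pregnancy rate of 0.1% for copper IUD EC users and a 1% EC pregnancy rate for LNG IUD users", a margin of 2.5%, 80% power and a two-sided 95% CI. With unpooled variance:

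n per arm = (1.96 + 0.8416)² × (0.001×0.999 + 0.010×0.990) / (0.025 − 0.009)² = 7.849 × 0.010899 / 0.000256 ≈ 334.2, rounded up to 335.

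Total 670; 670/0.95 = 705.3, rounded up to 706. Both figures match the plan. They were set for the pregnancy outcome. The documents give no SD, effect size or power for sexual satisfaction, so the 80% used below is only a reference point.

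**2. Baseline adjustment against a t-test on follow-up scores.** Assume a continuous score. Let r be the correlation between baseline and follow-up, which the documents do not give.

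- Standard error ratio, ANCOVA to t-test: sqrt(1−r²).
- Power of ANCOVA where the t-test has 80%: Φ((1.96 + 0.8416)/sqrt(1−r²) − 1.96).
- Difference detectable by t-test with 335 per arm at 80% power: sqrt(2 × 7.849/335) = 0.2165 SD. ANCOVA multiplies this by sqrt(1−r²).

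| Assumed r | SE ratio | Fall in SE | Power (from 80%) | Detectable difference (from 0.2165 SD) | n per arm matching a t-test on 335 |
|---|---|---|---|---|---|
| 0.2 | 0.980 | 2% | 82% | 0.2121 SD | 322 |
| 0.3 | 0.954 | 5% | 84% | 0.2065 SD | 305 |
| 0.5 | 0.866 | 13% | 90% | 0.1875 SD | 252 |
| 0.6 | 0.800 | 20% | 94% | 0.1732 SD | 215 |

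The ratios and powers do not depend on n. With 268 per arm (an assumed 20% loss from 335), the detectable difference at r = 0.5 goes from 0.2420 to 0.2096 SD.

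**3. If the t-test was meant on change scores.** With equal variances at the two times, the change-score variance is 2(1−r) times that of the follow-up comparison. The ANCOVA variance relative to it is (1−r²)/[2(1−r)] = (1+r)/2, which is 0.60, 0.65, 0.75 and 0.80 at the same four values of r. Below r = 0.5 the change score does worse than leaving the baseline out: at r = 0.3 its power is 65.8% where the follow-up t-test has 80%.

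**4. Simulation check.** With 335 per arm and 3,000 runs at each of r = 0.3, 0.5 and 0.7, the ANCOVA variance ratios were 0.92, 0.75 and 0.52 (formula: 0.91, 0.75, 0.51). The change-score ratios were 1.42, 1.00 and 0.61 (formula: 1.40, 1.00, 0.60).

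**5. Size of chance imbalance.** With 335 per arm the standard error of the baseline difference is sqrt(2/335) ≈ 0.08 SD. At r = 0.5 the shift it induces at follow-up has a standard error of about 0.5 × 0.08 = 0.04 SD.

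**The case against.** The strongest reply is that the t-test is a valid analysis and the outcome is peripheral. Both parts stand. No objective or hypothesis under Purpose and Objectives concerns sexual satisfaction, and the satisfaction named in Objective 3 is not described as sexual satisfaction. At low correlation the gain is slight. Even at r = 0.5 it is about 0.03 SD in the detectable difference.

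A reader might go further and infer that chance imbalance at baseline biases the device comparison. The documents do not support that. Allocation is randomized 1:1, so the unadjusted comparison of the randomized arms is unbiased and its confidence interval already covers chance imbalance.

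A reader might also infer that the plan definitely discards the baseline. It does not say so: the sentence on t-tests is generic, and a t-test on change from baseline would fit the outcome's wording. That reading weakens the point without removing it, because ANCOVA is still more precise for any r below 1.

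It can be argued that the closing words of the t-test sentence leave room for an adjusted model. They read more naturally as a choice between the two named tests. If adjustment is left open, it may be decided after the data are seen.

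Finally, the scale is not stated. If the item is ordinal, the standard-error formula does not carry over. That also stands, and it limits the figures to the continuous case.

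**Conclusion.** The point holds as a minor loss of efficiency in one secondary outcome. The plan lists a baseline value and names no analysis with a baseline term. Avoidable loss in the standard error runs from about 2% at r = 0.2 to 20% at r = 0.6, given a continuous score, a t-test on follow-up scores and an assumed r. If change scores were intended, the loss is the one in step 3 of the working instead. It is not a question of bias. The primary non-inferiority test, the 335 per arm and the total of 706 are untouched. Severity: optional.

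**What to change.** In Data Analyses, add a sentence for sexual satisfaction. First state the instrument, its scale and the time point to be compared, for example 12 months. Then compare the randomized arms with a linear model of the score at that time point, or a mixed model over the follow-up contacts, with arm and baseline score as terms. Report the adjusted difference with its 95% CI and show the unadjusted comparison alongside.

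If the item is ordinal, use a proportional-odds model with the same terms, and note that its odds ratio is conditional on baseline and that the sqrt(1−r²) figures do not apply.

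The cost is a sentence or two of text. No participants are added and the primary analysis does not change. Because the visit lists do not name the item, confirm that the enrollment and follow-up questionnaires collect it; if they do, no new data are needed.

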### Data Analyses:

The primary objective will be tested by non-inferiority design to test the hypothesis that the LNG IUD is no worse than the copper IUD with a noninferiority margin of 2.5%. Using Blackwelder's approach for equivalence testing,[8] comparing those who become pregnant during the menstrual cycle in which their study IUD was inserted. Noninferiority will be established if the lower bound of a two-sided 95% CI does not cross the noninferiority bound. Analysis will be by intention to treat.

For objective #2, comparison of one-year unintended pregnancy rates from women initiating the levonorgestrel IUD vs. copper T380 IUD for EC, will be assessed by Kaplan-Meier estimates. This same approach will be utilized to construct estimates of the proportion of patients who continue with their selected IUD for 1 year (continuation

proportion). Continuous variables will be assessed by t-tests and discrete variables by Chisquare testing as appropriate.

All data will be analyzed using Stata statistical software (College Station, Texas). Standard quality control methods will be employed including use of an independent data safety monitor.

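### The primary non-inferiority test names no interval formula, and the stated 80% power cannot be reached by any test that holds one-sided error at 2.5% at the planned rates

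*Combined protocol and SAP*

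**What the plan says.** The primary objective in the Data Analyses section tests whether "the LNG IUD is no worse than the copper IUD with a noninferiority margin of 2.5"%. The method is given as "Using Blackwelder's approach for equivalence testing,[8] comparing those who become pregnant during the menstrual cycle" of insertion, and the decision rule is "Noninferiority will be established if the lower bound of a two-sided 95% CI does not cross the noninferiority bound". Analysis is by intention to treat.

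The Sample Size and Randomization paragraph of the Statistical Methods section states "we assume a pregnancy rate of 0.1% for copper IUD EC users and a 1% EC pregnancy rate for LNG IUD users". It calls the LNG figure one that "is conservative, falling within the 95% confidence interval (CI) of 0%-5.2"% from an earlier study. It aims "To achieve 80% power to detect a twosided 95% CI around the EC pregnancy incidence" against the 2.5% margin, which "will require 335 participants per study arm (total of 670"). Recruitment is raised to 706 (353 per arm) for 5% early loss.

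Neither section states the variance estimator, any continuity correction, the interval formula, or what happens when an arm has no events. The sign of the difference behind the lower bound is also undefined. Objective 1, under Purpose and Objectives, gives a different margin of 1%.

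**The concern.** Normal-approximation intervals for a difference in proportions need a reasonable number of events. Here the plan expects 335 × 0.01 = 3.35 LNG pregnancies and 335 × 0.001 = 0.34 copper pregnancies. The chance of no copper pregnancy at all is 0.999^335 = 72%. With no events in either arm, the Wald interval has zero width.

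Two things are at stake. If the rule is the one implied by the sample-size formula, an LNG IUD that is truly 2.5 points worse would be declared non-inferior more than twice as often as the 95% CI implies. And because the interval is left open, it could be chosen after the counts are known, in a range of counts where that choice reverses the conclusion.

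**Working it through.** **Inputs.** From the Sample Size and Randomization paragraph: copper 0.1%, LNG 1%, margin 2.5 points, power 80%, two-sided 95% CI (one-sided 2.5%), 335 per arm, 353 per arm after the loss allowance. Paired figures below are for 335 and then 353 per arm, the latter meaning that every randomised woman has an outcome.

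**1. The plan's own figure.** With unpooled variance:

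n = (1.96 + 0.842)² × (0.001 × 0.999 + 0.01 × 0.99) / (0.025 − 0.009)² = 334.2, hence 335.

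The figure reproduces, and 670/0.95 rounds up to 706. Normal-approximation power is 80.1% at 335 and 82.1% at 353. This match is the reason for reading the analysis as an uncorrected, unpooled Wald interval.

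**2. Candidate rules.** The difference is LNG minus copper, and a trial passes if the upper limit is below 2.5%.
- Wald: d + 1.96 × √[(p₁(1−p₁) + p₀(1−p₀))/n].
- Corrected Wald: the same plus (1/n + 1/n)/2 = 1/n.
- Score (Miettinen-Nurminen): invert the score test, with the variance estimated under the constrained difference.

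Upper limits for plausible results:

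| n per arm | LNG v copper | Wald | Corrected | Score |
|---|---|---|---|---|
| 335 | 3 v 0 | 1.90% pass | 2.20% pass | 2.60% fail |
| 335 | 4 v 0 | 2.36% pass | 2.66% fail | 3.03% fail |
| 353 | 3 v 0 | 1.81% pass | 2.09% pass | 2.47% pass |
| 353 | 4 v 0 | 2.24% pass | 2.52% fail | 2.88% fail |

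At the planned rates, 35% of trials (335) or 22% (353) would pass Wald and fail score.

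**3. Exact error and power.** These sum the product of the two binomial probabilities over all pairs of counts that pass. Error is taken at LNG = copper + 2.5 points and power at 1% v 0.1%.

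| Rule | Error at 2.6% v 0.1% | Error range, copper 0–3% | Power |
|---|---|---|---|
| Wald | 6.6% / 6.4% | 3.0–7.7% / 2.9–6.4% | 76% / 76% |
| Corrected Wald | 3.6% / 2.7% | 1.8–3.6% / 1.9–2.8% | 62% / 59% |
| Score | 1.2% / 1.9% | 1.0–2.4% / 1.7–2.3% | 41% / 54% |

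**4. Ceiling for any method.** Take the single null point 2.6% v 0.1% against 1% v 0.1%. The copper rate is the same in both, so by Neyman-Pearson the most powerful 2.5% test passes on a low LNG count alone.
- At 335 per arm, P(LNG ≤ 3) is 2.47% under 2.6% and 56.9% under 1%. Spending the remaining error by randomising at a count of 4 adds 0.0083 × 18.5% = 0.15 points, giving 57.0%.
- At 353 per arm, P(LNG ≤ 3) is 1.77% and 53.0%. Randomising at 4 adds 0.249 × 19.1% = 4.7 points, giving 57.7%.

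A test that holds 2.5% over the whole null cannot beat these values. Enforcing the limit along the null boundary lowers the 335 figure to 54.2% and leaves 57.7% at 353.

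**5. Sensitivity to the LNG rate (copper 0.1%).** Score power is 60% / 73% at 0.75%, 81% / 90% at 0.5%, and over 99% if both rates are 0.1%. It reaches 80% at an LNG rate of about 0.51% / 0.66%.

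**6. If the 1% limit governs instead.** With 0 v 0 the score upper limit is 1.14% / 1.08%, so even no pregnancies would fail. Power at 1% v 0.1% is 15% / 13% for Wald and 1.0% / 0.9% for score. Wald error at 1.1% v 0.1% is 11.6% / 10.0%.

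**The case against.** The strongest reply is that the plan never says Wald. Sizing by a normal approximation and analysing by another method is common, and the cited reference, which was not available here, may prescribe a variance or a correction. With a continuity correction and 353 per arm, error at the planned copper rate is 2.7%, close to nominal. The 335 is correct arithmetic, and on the Wald reading power falls only from 80% to 76%. The larger shortfall appears once the test is replaced, and it depends on an LNG rate that the plan calls conservative. Finally, Miettinen-Nurminen is one choice among several, and its power moves in jumps at this size (39.6% at 348 per arm, 54.7% at 349).

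Much of this is fair. The 6.6% and 6.4% are conditional on an inference and are not an established property of the trial. Miettinen-Nurminen is a recommendation, not the only valid answer; a Newcombe interval gives nearly the same power (42% / 54%).

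The ceiling in step 4 does not depend on the inference, however. The plan ties its 80% to 1% v 0.1%, and at those rates no test with 2.5% error gets there. A more favourable LNG rate raises power but does nothing for error at the margin. And if the reference does settle the formula, the plan still needs to say so.

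**Conclusion.** The concern holds. The primary decision rule is under-specified where specification decides the result, and the stated 80% power is incompatible with the 2.5% one-sided error implied by the 95% CI at the plan's own rates and sample size. The best possible is about 58%, and a score interval gives 41% (335 evaluable per arm) to 54% (353).

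On the inferred uncorrected Wald reading, error is 6.6% / 6.4% at the planned copper rate and above 2.5% at every copper rate examined from 0 to 3%.

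All of this assumes a 2.5-point margin, independent binomial outcomes, 1:1 allocation, and power judged at 1% v 0.1%. This must be corrected before analysis.

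**What to change.** 1. Reconcile the 2.5% margin in the Statistical Methods and Data Analyses sections with the 1% limit in Objective 1. If 1% governs, every figure above except step 6 must be recomputed.
2. Replace the decision rule in Data Analyses with wording such as: *The difference is LNG minus copper pregnancy risk. Non-inferiority is claimed only if the upper limit of the two-sided 95% Miettinen-Nurminen score CI is below the non-inferiority margin.* This also settles the undefined sign.
3. In Sample Size and Randomization, restate exact power for that method at 1% v 0.1% as 41% (335 evaluable per arm) and 54% (353), and show how it varies with the LNG rate (0.75%: 60% / 73%; 0.5%: 81% / 90%).

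Correcting the rule costs a few sentences, with no extra participants or data, but the stated power becomes much less favourable. It does not restore 80% at 1% v 0.1%. That would take about 627 per arm, the size from which score power stays above 80% in a scan up to 759 per arm. The 850 given under Sample Size for all centers would yield 59%, assuming that all are randomised 1:1 (425 per arm) with outcomes. The documents do not say this, and the Statistical Methods section caps the study at 706.

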# **Purpose and Objectives**

In this prospective observational study, all women presenting for Emergency Contraception (EC) at Planned Parenthood Association of Utah (PPAU) clinics will be counseled using a standardized script; those interested in an IUD, who meet study qualifications and agree to participate, will be randomized to either the hormonal IUD (LNG 52mg IUD commonly known as Mirena® or Lilleta®) or the copper IUD (Paragard®). Participants will be followed for one year. If enrollment goals are not achieved due to a lack of willingness among potential participants to be randomized then we will initiate a PPC (patient preference cohort). In that case, participants who are interested in the study and eligible for participation but not willing to be randomized will be offered participation in a PPC.

This study has three specific objectives.

**Objective 1**: Determine the efficacy of the levonorgestrel IUD and copper T380 IUD for emergency contraception as assessed by urine pregnancy tests 1 month after EC use.

*Hypothesis*: The LNG IUD is non-inferior to the copper T380 IUD for EC based on a 1% non-inferiority limit.

**Objective 2**: Compare the one-year unintended pregnancy rates from women initiating the levonorgestrel IUD vs. copper T380 IUD for EC.

*Hypothesis*: At one-year the LNG IUD users will have lower pregnancy rates compared to copper IUD users.

**Objective 3:** Assess the one-year continuation, satisfaction, pain, and bleeding patterns of a LNG20 IUD to a copper T380 IUC as a method of EC and the mechanisms of continuation.

*Hypothesis*: The LNG IUD will have superior rates of continuation and non-inferior satisfaction (what about pain and bleeding patterns) compared to the copper IUD as a method of EC and the mechanisms of continuation.

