#### **Inclusion Criteria:**

Eligible participants must be:

- 1. Between 18-35 years old
- 2. In need of EC (had unprotected intercourse within 120 hours 5 days)
- 3. Desire to prevent pregnancy for 1 year
- 4. Fluent in English and/or Spanish
- 5. Have a regular menstrual cycle (21-35 days)
- 6. Know their last menstrual period (+/-3 days)
- 7. Be willing to comply with the study requirements

8. Participants current preferred phone number must be functioning at the time of study entry and will be tested prior to enrollment

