### Enrollment (Initial Clinic Visit)

- Consent process
- Urine pregnancy test (Completed at the Planned Parenthood Clinic Lab)
- Assignment to either randomized arm or PPC arm
- IUD Insertion
- Data collection
- Diary instructions
- Gonorrhea/Chlamydia testing, if recommended per PPAU STI screening protocols

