### 1 Month Follow-Up

- The 1 month follow-up appointment will be made on the day of enrollment. Urine pregnancy test and confirmation of IUD position will be conducted at the clinic. An IUD string check may also be performed.
  - Participants will be asked to complete a home pregnancy test on the day before their 1 month clinic visit that will be given to them at their enrollment visit. They will be asked to take a picture of the pregnancy test results and text the results picture to a dedicated Planned Parenthood clinic cell phone (number will be provided at the time of enrollment). This at-home testing will be confirmed at the in-clinic appointment as a proof-of-concept to establish this as a norm for future studies with the goal of reducing participant burden.
- The following information will also be obtained either at the 1 month follow-up appointment or by phone, text, or email link to an online data collection instrument for those participants not able to return to clinic for the 1 month follow-up.
  - Bleeding history
  - Sexual activity
  - Data collection including evaluation of satisfaction of method chosen, current use of contraception and review for potential adverse events
- If urine pregnancy test is positive, the following will occur:
  - Ultrasound and/or serum quantitative hCG pregnancy test as necessary to date the pregnancy (this will be completed at the Planned Parenthood Clinic Lab)
  - Removal of IUD
  - o Follow-up throughout remainder of pregnancy
  - Pregnancy options counseling and appropriate referral for pregnancy care based on desire to continue or terminate the pregnancy.

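### Does the plan give the primary event two competing definitions: a positive 4-week test, and a pregnancy in the insertion cycle?

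*Combined protocol and SAP*

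**What the plan says.** Three places describe the primary event.

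- Purpose and Objectives, Objective 1: efficacy of each device "as assessed by urine pregnancy tests 1 month after EC use".
- Outcomes, Primary Outcome: failures of emergency contraception in both arms, assessed by "positive urine pregnancy tests (HCG >25 IU) 4 weeks after having the IUD inserted".
- Data Analyses, primary objective: a non-inferiority comparison with a 2.5% margin, "comparing those who become pregnant during the menstrual cycle in which their study IUD was inserted".

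Other sections supply the information needed to place a pregnancy in time. Under Inclusion Criteria a woman must "Have a regular menstrual cycle (21-35 days)" and "Know their last menstrual period (+/-3 days)". The enrolment visit includes "Urine pregnancy test (Completed at the Planned Parenthood Clinic Lab)", and current pregnancy is an exclusion. After a positive test at one month, the 1 Month Follow-Up section provides for "Ultrasound and/or serum quantitative hCG pregnancy test as necessary to date the pregnancy".

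No section says in words that a positive test dated outside the insertion cycle is, or is not, a primary event.

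**The concern.** Taken literally, the first two descriptions set no condition on when conception occurred, and the third does. Cycles of 21 to 35 days are eligible and no section restricts the cycle day of insertion. A woman whose device is placed late in her cycle is therefore well into the next cycle at four weeks. A positive test dated to that next cycle would be an event under Objective 1 and Outcomes but not under Data Analyses.

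The stake is the smallness of the event count. If a single pregnancy can move the confidence limit across the margin, an unwritten rule for counting a borderline pregnancy could be settled after its effect is known.

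**Working it through.** **The plan's own figure.** Inputs from Sample Size and Randomization: 0.1% (copper), 1% (LNG), margin 2.5%, 80% power, two-sided 95% interval.

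n per arm = (1.960 + 0.842)² × (0.001 × 0.999 + 0.01 × 0.99) / (0.025 − 0.009)² = 7.849 × 0.010899 / 0.000256 = 334.2, so 335. With 5% loss, 670 / 0.95 = 705.3, so 706. Both agree with the plan. The two wordings do not affect this calculation. (Objective 1 gives a 1% limit; that is a separate matter, and 2.5% is used here.)

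**How fragile the result is.** Expected events are 335 × 0.01 = 3.35 (LNG) and 335 × 0.001 = 0.335 (copper), 3.685 in all. The upper 95% Wald limit (assumed method) for LNG minus copper is d + 1.96 × √[(p₁(1 − p₁) + p₂(1 − p₂)) / 335].

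| LNG v copper events | Upper limit | Margin 2.5% |
|---|---|---|
| 4 v 0 | 2.36% | met |
| 5 v 0 | 2.79% | not met |
| 4 v 1 | 2.20% | met |
| 5 v 1 | 2.62% | not met |
| 5 v 2 | 2.43% | met |
| 6 v 2 | 2.84% | not met |

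Summed over copper counts under the planning rates, the chance of landing on the last LNG count that passes is 18.2%. That is the chance that one extra LNG event would matter, not the chance that one arises.

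**How often the wordings can differ.** Assumptions not in the documents: ovulation 14 days before menses, a positive test 12 days later, and every insertion day equally likely. Let cycle length c run from 21 to 35, insertion day i from 1 to c (420 combinations), and the test fall on day i + 28.

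- Next-cycle conception already positive: c + (c − 14) + 12 ≤ i + 28. This holds in 55 of 420 (13.1%), all with c ≤ 30. If each cycle length has equal weight, the share is 15.4%.
- Insertion-cycle conception still negative: (c − 14) + 12 > i + 28. This holds in 10 of 420 (2.4%), with c = 32 to 35 and i = 1 to 4. Insertion is then 17 to 20 days before modelled ovulation, so these would hardly be failures of EC for intercourse in the preceding 120 hours.
- Conception in the cycle before enrolment: modelled at 15 days before day 1 and test-positive 3 days before day 1. The enrolment test should exclude most of these.

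**How many pregnancies that is.** A next-cycle event also needs conception after the device is placed. Assume annual IUD failure f of 0.2% to 2% in both arms and 13 cycles a year. Additions per arm = 335 × share × f / 13.

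- Low: 335 × 0.131 × 0.002 / 13 = 0.0067 per arm, 0.013 in the trial.
- High: 335 × 0.154 × 0.02 / 13 = 0.0795 per arm, 0.159 in the trial.

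**Effect on the conclusion.** Enumerating binomial event counts, with Poisson additions in both arms, reverses the conclusion in 0.14% of trials (low) to 1.67% (high). A rough check on the high figure is 0.0795 × 0.182 = 1.4%. Most of the rest comes from added copper events turning a fail into a pass, such as 5 v 1 becoming 5 v 2.

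**The case for a change.** The strongest case for a change is that discordance, though rare, is cheap to rule out. With about four events, a rule is most credible if written before outcomes are known. The plan dates pregnancies only where necessary, and does not say who decides or what happens when a date is uncertain. That much is true, and a clarifying sentence would do no harm.

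The rest carries less weight.

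- *Severity.* If out-of-cycle pregnancies added 0.25% in both arms, approximate power would fall from 0.80 to 0.64. But that is 670 × 0.0025 = 1.7 pregnancies, about ten times the largest figure derived above.
- *Bias in dating.* The 1 Month Follow-Up section lists dating alongside "Removal of IUD", so the person dating might see the device. The section does not say that this person classifies the endpoint. The risk is conceivable, not documented.
- *A ready-made calendar rule.* Ending the insertion cycle at the next expected menses would drop a late-ovulation conception that the Data Analyses wording counts. A mechanical rule could therefore introduce an error of its own.
- *The home test.* Whether a texted result can replace a missed clinic test is a question about missing outcomes. It has no bearing on cycle assignment.

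**Conclusion.** No change follows. The Outcomes section does not make every positive test an event in its own right. It names failure of emergency contraception and says how that is assessed. Data Analyses identifies the cycle to which such a failure belongs, and the follow-up section provides the dating. Read together, these are one concept, its measurement and its timing. An analyst would date each of the roughly four expected pregnancies from the last menstrual period, cycle length and dating results, and could report any that fell outside the insertion cycle.

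The gap that remains is an unwritten classification detail. Its size is 0.01 to 0.16 pregnancies in the trial, with a reversed conclusion in about 0.1% to 1.7% of trials. Those figures rest on the fixed-ovulation timing model, a Wald interval, the planning rates and an assumed annual failure of 0.2% to 2%. They leave out conceptions after early expulsion or removal, so they indicate scale and are not a strict bound. Confidence is high that no explicit linking rule exists, and equally that following the plan as written would still give a sound primary result on this point.
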